6.2.4 Duration/Study Day/Time

Study day will be calculated as the number of days from the dose of lemborexant on Day 1 using the following rules:

- date of event – date of first dose + 1, for events on or after first dose
- date of event – date of first dose, for events before first dose.

6.2.5 Conventions for Missing and Partial Dates

All dates presented in the individual subject listings will be as recorded on the electronic case report form (eCRF).

6.2.6 Unscheduled Visits

Only scheduled post baseline laboratory and vital signs values will be tabulated. Post baseline repeat/unscheduled assessments will be disregarded unless otherwise stated, although these post baseline assessments will be listed in Appendix 16.2.

6.2.7 Potential Cataplexy AEs

Potential AEs of Cataplexy are identified as those AEs with a verbatim term coded to one of the following MedDRA preferred terms:

Cataplexy	Dysarthria	Apallic syndrome	Presyncope
Muscle fatigue	Slow speech	Consciousness fluctuating	Transient ischaemic attack
Muscular weakness	Heteronymous diplopia	Depressed level of consciousness	Amaurosis fugax
Muscular tone disorder	Homonymous diplopia	Lethargy	Capsular warning syndrome
Hypotonia	Eyelid myoclonus	Loss of consciousness	Reversible ischaemic neurological deficit
Drop attack	Myoclonus	Sopor	
Slurred speech	Opsoclonus myoclonus	Stupor	
Diplopia	Clonus	Transient global amnesia	
Falls	Altered state of consciousness	Syncope	

Such AEs are identified on the eCRF by an answer of ‘Yes’ to the question ‘Potential Cataplexy AE?’.

6.3 Conventions

All data listings, summaries, figures and statistical analyses will be generated using SAS¹ version 9.4 or higher or Phoenix™ WinNonlin® (Version 6.3 or later, Certara USA, Inc., Princeton, NJ).

Listings will be sorted in the following order: renal function group, subject, parameter, and day, unless otherwise stated. All data will be listed.

Continuous variables will be summarized by the number of nonmissing observations, mean, median, standard deviation (SD), and minimum and maximum. For all tabulations of changes from baseline data, the lower and upper 95% confidence limits for the mean for the individual treatments will be given. In addition, PK parameter data will have the geometric mean and coefficient variation (CV%) presented. CV% will be calculated as $\sqrt{\exp[\text{SD}^2 \text{ of log transformed data}] - 1} * 100$.

Categorical variables will be summarized by presenting the frequency and percent. Percentages will be based on the number of nonmissing observations or the subject population unless otherwise specified. For each variable, all categories will be shown. Zero frequencies (but not the percent) within a category will be presented.

6.3.1 Decimal Places

For pharmacokinetic data, when presenting individual/raw (raw, hereafter) values and summary statistics, the following rules will be applied: for drug concentrations and concentration-dependent pharmacokinetic parameters, all summary statistics (mean, median, geometric mean, SD, and CV%) will have 3 significant digits. For t_{max} , raw values and summary statistics will be presented to 2 decimal places.

The adjusted regression coefficient (R^2 adj) will be presented to 3 significant digits. The number of time points used in the lambda-z estimates will be presented as an integer number. Lower and upper times of the lambda-z range will be presented to the same precision as the actual sampling time after dosing used for the calculation of PK parameters.

For all other data, means, medians and percentiles will be displayed to one more decimal place than the data, dispersion statistics (e.g. standard deviation) will have two more decimal places, and the minimum and maximum will be displayed to the same number of decimal places as reported in the raw data. Percentages will be displayed with one decimal place.

6.4 Subject Disposition

Subject disposition will be listed and summarized as follows:

- The number of subjects who are in each analysis set will be summarized for all enrolled subjects by renal function group and overall.
- The number of subjects who failed screening and the reasons for failure will be tabulated overall.
- The number of subjects who complete the study will be tabulated for all enrolled subjects by renal function group and overall.
- The number of early terminations and the primary reasons for terminations will be tabulated for all enrolled subjects by renal function group and overall. Secondary reasons for termination will be listed.
- Disposition data for all subjects screened will be listed.

6.5 Protocol Deviations

A listing of protocol deviations will be provided within Appendix 16.2. Protocol deviations will be categorized as either major or minor by Eisai prior to database lock.

6.6 Inclusion and Exclusion Criteria

A listing of violators of the inclusion and exclusion criteria will be provided within Appendix 16.2.

6.7 Baseline Assessments

Standard continuous or categorical variable summaries will be presented by renal function group and overall for the following variables based on the Safety Analysis Set.

- Demographic data, data for all screened subjects will be listed.
- Weight at screening (kg)
- Height at screening (cm)
- BMI at screening (kg/m²)
- eGFR (mL/min/1.73 m²) at Day -1

6.8 Medical History

Medical and surgical history and current medical conditions will be recorded at the Screening Visit. Separate listings of previous and ongoing conditions at screening will be presented for the Safety Analysis Set. Conditions will be coded using the Medical Dictionary of Regulated Activities (MedDRA) primary system organ class and preferred term.

6.9 Prior and Concomitant Medications

All investigator terms for medications recorded in the CRF will be coded to an 11-digit code using the World Health Organization Drug Dictionary (WHO DD) drug codes. Non pharmacological procedures will be recorded in the CRF but not coded. Prior and concomitant medications will be listed. Prior medications will be defined as medications that stopped before the first dose of lemborexant. Concomitant medications will be defined as medications that started after the date of the first dose of study drug.

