Group 1 subjects (severe renal impairment) will be enrolled first. Group 2 subjects (normal renal function) will be matched according to age, race, sex, and BMI.

Subjects determined eligible for study participation will receive a single 10 mg oral dose of lemborexant on Day 1. During the Treatment Period, plasma will be obtained over 11 days for the determination of lemborexant and metabolite concentrations M4, M9 and M10. Standard safety assessments will be measured before, during, and at the conclusion of the study.

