12 LIST OF TABLES, FIGURES AND LISTINGS

Please note: Table, Listing, and Figure titles are subject to change upon final analysis. Tables, Listings, and Figures may be consolidated as necessary.

Table Number	Table Title
14.1.1	Subject Disposition
14.1.1.1	Subject Disposition Enrolled Subjects
14.1.1.2	Screening Failures
14.1.3	Demography, Baseline Characteristics, Treatment Compliance, and Analysis Populations
14.1.3.1	Datasets Analyzed Enrolled Subjects
14.1.4.1.1	Demography and Baseline Characteristics Safety Analysis Set
14.2	PK Analysis
14.2.2.1	Descriptive Statistics for Lemborexant and Metabolites Concentration-Time Data after Administration of Lemborexant 10 mg to Subjects with Severe Renal Impairment (Group 1) or Normal Renal Function (Group 2) PK Analysis Set
14.2.2.2	Descriptive Statistics for Bound and Unbound Fraction (%) of Lemborexant and Metabolites in Plasma after Administration of Lemborexant 10 mg to Subjects with Severe Renal Impairment (Group 1) or Normal Renal Function (Group 2) PK Analysis Set
14.2.2.3	Descriptive Statistics for the Unbound Fraction of Lemborexant and Metabolites in Plasma after Administration of Lemborexant 10 mg to Subjects with Severe Renal Impairment (Group 1) or Normal Renal Function (Group 2) PK Analysis Set
14.2.2.4	Descriptive Statistics for the Unbound Fraction (%) of Lemborexant and Metabolites in Plasma after Administration of Lemborexant 10 mg to Subjects with Severe Renal Impairment (Group 1) or Normal Renal Function (Group 2) with Averaged Time Points (1h and 24h) PK Analysis Set
14.2.2.5	Descriptive Statistics for the Unbound Fraction of Lemborexant and Metabolites in Plasma after Administration of Lemborexant 10 mg to

- Subjects with Severe Renal Impairment (Group 1) or Normal Renal Function (Group 2) with Averaged Time Points (1h and 24h)
PK Analysis Set
- 14.2.3.1 Descriptive Statistics for Pharmacokinetic Parameters of Lemborexant after Administration of Lemborexant 10 mg to Subjects with Severe Renal Impairment (Group 1) or Subjects with Normal Renal Function (Group 2)
PK Analysis Set
- 14.2.3.2 Descriptive Statistics for Pharmacokinetic Parameters of M4 after Administration of Lemborexant 10 mg to Subjects with Severe Renal Impairment (Group 1) or Subjects with Normal Renal Function (Group 2)
PK Analysis Set

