14.2.2.6	Box Plot of Lemborexant and Metabolites C_{max} Values after Administration of Lemborexant 10 mg to Subjects with Severe Renal Impairment (Group 1) or Normal Renal Function (Group 2) PK Analysis Set
14.2.2.7	Box Plot of Lemborexant and Metabolites $AUC_{(0-8h)}$ Values after Administration of Lemborexant 10 mg to Subjects with Severe Renal Impairment (Group 1) or Normal Renal Function (Group 2) PK Analysis Set
14.2.2.8	Box Plot of Lemborexant and Metabolites $AUC_{(0-72h)}$ Values after Administration of Lemborexant 10 mg to Subjects with Severe Renal Impairment (Group 1) or Normal Renal Function (Group 2) PK Analysis Set

- 14.2.2.9 Box Plot of Lemborexant and Metabolites $AUC_{(0-t)}$ Values after Administration of Lemborexant 10 mg to Subjects with Severe Renal Impairment (Group 1) or Normal Renal Function (Group 2)
PK Analysis Set
- 14.2.2.10 Box Plot of Lemborexant and Metabolites $AUC_{(0-inf)}$ Values after Administration of Lemborexant 10 mg to Subjects with Severe Renal Impairment (Group 1) or Normal Renal Function (Group 2)
PK Analysis Set
- 14.2.2.11 Protein Binding (Percent Bound) Box Plots Comparing PBE2006A, PBM4A, PBM9A and PBM10A Values after Administration of Lemborexant 10 mg to Subjects with Severe Renal Impairment (Group 1) or Normal Renal Function (Group 2) for 1h and 24h
PK Analysis Set
- 14.2.2.12 Scatterplots for Pharmacokinetic Parameters of Lemborexant and Metabolites versus Group
PK Analysis Set
- 14.2.2.13 Scatterplots for Pharmacokinetic Parameters Adjusted by Unbound Fraction in Plasma for Lemborexant and Metabolites versus Group
PK Analysis Set
- 14.2.2.14 Scatterplot and Regression Analysis for Pharmacokinetic Parameters of Lemborexant and Metabolites versus eGFR at Day -1
PK Analysis Set

Listing Number	Listing Title
16.2.1	Subject Disposition
16.2.1.1	Subjects Disposition Enrolled Subjects
16.2.2	Protocol Deviations
16.2.2.1	Protocol Deviations Safety Analysis Set
16.2.2.2	Inclusion/Exclusion Not Met
16.2.3	Demography, Baseline Characteristics, Treatment Compliance, and Analysis Populations
16.2.3.1	Analysis Populations Enrolled Subjects
16.2.4.1	Demographics Enrolled Subjects
16.2.4.2	Previous Medical History Safety Analysis Set
16.2.4.3	Ongoing Medical History Safety Analysis Set
16.2.4.4	Prior Medications Safety Analysis Set
16.2.4.5	Concomitant Medications Safety Analysis Set
16.2.5.1	Dosing Information Safety Analysis Set
16.2.6	PK

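### Does it matter that SAP Section 6.9 gives no category to a medication already being taken when lemborexant is dosed?

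*SAP*

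**What the plan says.** Section 6.9 of the SAP gives two definitions. The first turns on the stop: "Prior medications will be defined as medications that stopped before the first dose of lemborexant". The second turns on the start: "Concomitant medications will be defined as medications that started after the date of the first dose of study drug". The only output planned there is a listing: "Prior and concomitant medications will be listed". Section 12 accordingly has two medication listings, 16.2.4.4 ("Prior Medications Safety Analysis Set") and 16.2.4.5 ("Concomitant Medications Safety Analysis Set"), and no medication table.

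Three other statements bear on the point. The Introduction (Section 1) fixes a single dose: "Subjects determined eligible for study participation will receive a single 10 mg oral dose of lemborexant on Day 1". The first dose is therefore the only dose, and its date is Day 1. Section 6.3 says without qualification that "All data will be listed". The note opening Section 12 says that "Tables, Listings, and Figures may be consolidated as necessary".

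**The concern.** The two definitions use different variables, so together they do not cover every record. A medication begun before Day 1 and still taken at dosing did not stop before the dose and did not start after the dose date. Read literally, it is neither prior nor concomitant. Because the second definition refers to the date of the dose, a medication begun on Day 1 after the dose is left out as well.

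The drugs left out are not trivial ones. Group 1 has an eGFR below 30, so long-term therapy is plausible, although the SAP gives no frequency. A drug on board at a single dose is what a reader would look for when interpreting a difference in lemborexant exposure between the groups, or an adverse event. If such records dropped out of both listings, the reader of the study report would lose that information.

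**Working it through.** There is no figure in the SAP to reproduce. The check has two steps: confirm the gap, then trace where the categories are used.

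**Step 1: is there a gap?** Apply the two definitions to five start and stop patterns around the Day 1 dose.

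| Pattern | Stopped before the dose? | Started after Day 1? | Category |
|---|---|---|---|
| Started and stopped before the dose | yes | no | prior |
| Started before the dose, stopped Day 5 | no | no | neither |
| Started before the dose, still ongoing at study end | no | no | neither |
| Started Day 1 after the dose | no | no | neither |
| Started Day 3 | no | yes | concomitant |

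Two of the five are classified and three are not. A finer grid uses four time windows: before Day 1, Day 1 before the dose, Day 1 at or after the dose, and later. With the stop not earlier than the start, it has 4 + 3 + 2 + 1 = 10 patterns, of which 3 are prior, 1 is concomitant and 6 are neither. The gap is real on either grid. The proportions, 3 of 5 or 6 of 10, depend only on how time is divided. They say nothing about how many subjects are affected.

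**Step 2: what uses the categories?**

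- *Analysis sets (Section 6.1).* Membership of the PK and Safety sets depends on dosing and on having PK or safety data, not on medications.
- *Baseline tables (Section 6.7).* These cover demographic data, weight, height, BMI and eGFR. Medications are not tabulated.
- *PK comparison (Section 6.15).* The linear model has renal impairment group as its factor, and the follow-on regression has Day -1 eGFR as its independent variable. Medication is not a term in either.
- *Adverse events (Section 6.17.1).* Treatment emergence is judged against the state at Baseline, and relatedness comes from the recorded assessment. Neither uses the medication category.
- *Protocol deviations (Section 6.5).* The sponsor categorizes these before database lock. The section makes no reference to the prior or concomitant label.
- *Listings (Section 12).* Only 16.2.4.4 and 16.2.4.5 use the split.

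The gap therefore decides which listing a record sits in and nothing else.

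**Step 3: can the record disappear?** Section 6.9 codes every medication term recorded in the CRF, with no restriction by category, and Section 6.3 requires all data to be listed. A program that dropped a continuing drug from both listings would break Section 6.3. The Section 12 note also allows the two listings to be merged. What remains open is the heading, not whether the record is visible.

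**The case for a change.** The strongest case for a change is that neither rescue assigns a category. The listing rule in Section 6.3 states an intention, and consolidation is optional, so someone programming Section 6.9 literally could leave these records out of both outputs. The SAP also handles the same boundary properly elsewhere. Section 6.8 separates previous from ongoing conditions, the study-day rule in Section 6.2.4 includes the day of dosing, and the treatment-emergent definition in Section 6.17.1 deals with events already present. A continuing illness thus has a defined listing while the drug treating it does not. That points to an oversight rather than a choice, and correcting it would take one sentence.

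Most of this stands as a description of the text: the definitions are incomplete, and nothing in the SAP defends them. It does not show that a result is at risk. The harm described needs a programmer to follow Section 6.9 to the letter while ignoring Section 6.3, and a reviewer of the listings not to notice that no continuing medication appears.

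A tighter rule would also bring questions of its own. Splitting Day 1 records at the time of dosing needs medication clock times, which the SAP does not say are collected; Section 6.2.5 speaks only of dates as recorded. Closing the concomitant window at the Day 11 visit would leave any later recorded medication unclassified, whereas the present wording classifies it as concomitant.

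**Conclusion.** The gap in Section 6.9 is real, but it is a drafting slip with no bearing on the results, and no change to the plan is called for. An analyst would ordinarily treat a medication continuing at dosing, or begun after it, as concomitant, and Section 6.3 already obliges the record to be shown.

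The number of subjects affected is not given. It could be anything from 0 to all 8 planned in a group, and the conclusion is the same throughout that range: no geometric mean ratio, confidence interval, summary table or adverse event count changes.

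This rests on two assumptions: that the instruction to list all data is followed, and that no output outside those planned in the SAP uses the medication categories. The protocol was not available and may define the terms more fully, but the conclusion does not depend on it.

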6.10 Viral Serology

A listing of viral serology results will be provided within Appendix 16.2.

6.11 Urine drug and alcohol screening

A listing of urine drug and alcohol screening results will be provided within Appendix 16.2.

6.12 Pregnancy Test

A listing of serum and urine pregnancy test results will be provided within Appendix 16.2.

6.13 Exposure to Study Drug

A listing of dosing information will be provided within Appendix 16.2.

6.14 Efficacy Analyses

Not Applicable

6.15 Pharmacokinetic Analysis

The Safety Analysis Set will be used for individual plasma concentration listings. The PK Analysis Set will be used for summaries of plasma concentrations and for analyses, summaries, and listings of PK parameters.

Blood samples (4 mL each) for PK assessments of lemborexant and its metabolites (M4, M9, and M10) will be collected at predose (0 hour), 0.5, 1, 1.5, 2, 3, 4, 6, 8, 12, 24, 36, 48, 72, 96, 120, 144, 168 and 240 hours postdose. In addition, blood samples for protein binding (12 mL per time point) of lemborexant will be collected at 1 and 24 hours postdose matching the PK sample collection at those time points.

For presentation of the individual data, BLQ values prior to the first non-zero concentration will be set to zero in the linear plots; BLQ values after the first non-zero concentration will be set to missing in the linear plots; and all BLQ values will be set to missing in the semi-logarithmic plots.

For calculation of mean concentrations, all BLQ values will be assigned as zero. If the proportion of values reported as BLQ is more than 50% or if the calculated mean is less than the lower limit of quantification (LLOQ) at a given sampling time, the mean will be treated as follows: zero for time points prior to the first non-zero mean concentrations in the linear plots; missing for time points after the first non-zero mean concentration in the linear plots; and missing for all BLQ values in the semi-logarithmic plots.

Plasma concentration data will be tabulated by nominal time and summarized by analyte and group using descriptive statistics [number of observations (n), arithmetic mean, standard deviation (SD), minimum (min), median and maximum (max)].

Mean plasma concentration-time data (using linear and semi-logarithmic scales) will be presented graphically; mean data will be plotted using nominal sample times. Additionally, mean profiles will be presented with the x-axis truncated to 24 hours postdose.

PK parameters for lemborexant and its metabolites (M4, M9, and M10) will be calculated as described in Section 6.2.2.

The adjusted regression coefficient (R^2 adj), number of time points used in the lambda-z estimates, and the lower and upper times of the lambda-z range will also be listed.

PK parameters will be summarized overall by treatment and by treatment stratified by analyte and group using descriptive statistics (n, mean, SD, min, median, max, geometric mean, CV%, calculated as: $\sqrt{\exp[\text{std}^2 \text{ of log transformed data}] - 1} * 100$).

The rules for presenting raw individual values and summary statistics for PK concentration and parameter data are provided in Section 6.3.1.

Protein Binding

Blood samples for plasma protein binding for lemborexant and metabolites will be collected for each subject at 2 time points: 1 hour and 24 hours postdose. Protein binding data will be provided by the vendor to Worldwide Clinical Trials as a percentage; if more than one value is available for either time point, the average of the protein binding values will be used in the calculations. Protein binding results will be presented as fractions and percentages and will be summarized for each time point (1 hour and 24 hour). Additionally, the average of the 2 timepoints (1 hour and 24 hour) will be calculated for each subject and summarized. The average of the 1 hour and 24 hour timepoints will be used to calculate the unbound PK parameters (AUC_u and CL_u/F).

Protein binding results for 1 h and 24 h will be summarized using the following descriptive statistics: n, mean, SD, minimum, median, and maximum. Protein binding results (averaged timepoints at 1 h and 24 h) will be summarized using the following descriptive statistics: n, mean, SD, CV%, minimum, median, maximum, and geometric mean.

Box plots will be created for the percent bound comparing lemborexant and metabolites across groups. Scatterplots will also be created for lemborexant and metabolite AUC_u adjusted by the unbound fraction in plasma.

Evaluation of the impact of renal impairment on drug exposure:

The effect of renal impairment on the PK of lemborexant will be assessed using a linear model with renal impairment group as a factor. Logarithmically transformed values of the primary PK parameters C_{\max} , AUC_(0-8h), AUC_(0-72h), AUC_(0-t), and AUC_(0-inf) will be utilized to estimate the geometric mean ratio (and two-sided 90% confidence intervals) of subjects with severe renal impairment versus subjects with normal renal function. Similar statistical analyses will be conducted for the PK parameters of the metabolites and unbound lemborexant. In addition,

summary statistics for PK parameters in each renal function group will be tabulated. Box plots will be provided. The relationship between each of the PK parameters and the estimated renal function will be also presented graphically through the use of scatterplots of each PK parameter.

If the 90% confidence intervals indicate that there is an effect of renal impairment on the primary PK parameters, relationships between the individual subject PK parameters (C_{max} , $AUC_{(0-8h)}$, $AUC_{(0-t)}$, $AUC_{(0-72)}$, $AUC_{(0-inf)}$, and CL/F , both free and total) and individual subject estimated renal function (eGFR estimated by the MDRD) will be explored utilizing linear regression models with the PK parameter as the dependent variable and eGFR at Day -1 as the independent variable. Point estimates and 95% CIs of the intercept and slope will be presented.

